OFFICIAL TITLE: Twelve-Month Prospective Evaluation of Clinical and Radiographic Outcomes of Pulpotomy Materials in Primary Molars

NCT Number: not yet assigned

Document Date: June 28, 2025

1. Background

Pulpotomy is a widely accepted treatment modality for cariously exposed primary molars. While several medicaments have shown favorable outcomes, the comparative effectiveness of emerging and traditional materials within the same patient cohort remains understudied. This study aims to prospectively evaluate the clinical and radiographic outcomes of four pulpotomy medicaments—MTA, Biodentine, Ferric Sulfate, and Sodium Hypochlorite—using a split-mouth randomized controlled trial design over a 12-month period.

2. Study Objectives

Primary Objective: To compare the 12-month clinical and radiographic success rates of MTA, Biodentine, Ferric Sulfate, and Sodium Hypochlorite in pulpotomy treatment of primary molars.

Secondary Objective: To determine the feasibility and effectiveness of a split-mouth design for pulpotomy comparisons in pediatric patients.

3. Study Design

Design Type: Prospective, split-mouth, randomized controlled clinical trial.

Participants: Healthy children aged 4–7 requiring pulpotomy in four primary molars due to deep caries.

Sample Size: A priori power analysis determined that at least 19 patients were required to detect statistically significant differences.

Randomization: Performed at the tooth level within each patient using sealed opaque envelopes prepared by an independent researcher. Clinical and radiographic assessors were blinded to treatment groups.

Inclusion Criteria:

- Age between 4 and 7 years
- Four primary molars indicated for pulpotomy due to deep caries
- Clinical signs of reversible pulpitis only
- Restorable teeth with normal periapical radiographs

Exclusion Criteria:

- Systemic illness
- Teeth with signs of irreversible pulpitis or radiographic pathology
- Uncooperative behavior impeding treatment

5. Interventions and Procedures

Local Anesthesia: 2% Lidocaine with 1:100,000 epinephrine

Isolation: Rubber dam

Access: High-speed handpiece with sterile water-cooled diamond bur

Coronal Pulp Removal: Low-speed round bur

Hemostasis: Achieved with sterile water-moistened cotton pellet

Groups and Materials:

Group I: 15.5% Ferric Sulfate – 15 s application

Group II: 5.25% Sodium Hypochlorite Gel – 1 min application

Group III: MTA – ~2 mm thick layer

Group IV: Biodentine – full chamber fill

Restoration:

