Groups I-III: IRM base + stainless steel crown

Group IV: Biodentine fill + stainless steel crown

All crowns cemented with glass ionomer cement (Fuji I)

All procedures were performed by a single experienced pediatric dentist.

6. Follow-up and Outcome Measures

Follow-up Schedule:

Clinical: 3, 6, and 12 months

Radiographic: 6 and 12 months

Success Criteria:

Clinical: No pain, swelling, abscess, fistula, percussion sensitivity, or mobility

Radiographic: No furcation/periapical pathology, no internal resorption; Pulp canal obliteration was not deemed a failure

Evaluator Blinding:

- Clinical evaluation by two independent, blinded pediatric dentists
- Radiographic evaluation by a blinded pediatric dentist and radiologist

Disagreements were resolved through consensus. No pulp chamber masking was done, introducing a possible bias.

7. Statistical Analysis

All statistical analyses were performed using the Statistical Package for the Social Sciences (SPSS Version 26; IBM Corp., Armonk, NY, USA). Fishers exact test was used to compare clinical and radiographic outcomes at the 6- and 12-month follow-ups among the four groups. Success and failure rates were calculated based on a per-protocol analysis, which included 22 patients per group. Patients who did not complete the study protocol were excluded from the analysis. In addition, Cochrans Q test was applied to compare the clinical and radiographic success rates of the four pulpotomy materials (Biodentine, MTA, NaOCl, and Ferric Sulfate) at the 12-month follow-up. Treatment outcomes were dichotomized as success or failure. The test was calculated using data from all 22 patients in each group. The significance level was set at $p < 0.05$.

8. Ethical Considerations

Approval was obtained from Interventional Clinical Research Ethics Committee, (Approval No: 2021/77).

Written informed consent was obtained from the parents/legal guardians of all participants.

The study adhered to the Declaration of Helsinki and national regulations on human research ethics.

9. Data Handling and Confidentiality

All data will be anonymized and stored securely in password-protected databases accessible only to the research team. Personal identifiers will be removed during data analysis and reporting.

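### Each 12-month outcome gets an unmatched and a matched four-material test with neither decisive, and no matched comparison of pairs of materials is planned

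*Combined protocol and SAP*

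**What the plan says.** Section 2 gives one primary objective with two outcomes, neither ranked above the other: "To compare the 12-month clinical and radiographic success rates of MTA, Biodentine, Ferric Sulfate, and Sodium Hypochlorite in pulpotomy treatment of primary molars". Section 3 describes a split-mouth trial in which randomization was "Performed at the tooth level within each patient using sealed opaque envelopes".

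Section 7 then names two tests. The first is unmatched: "Fishers exact test was used to compare clinical and radiographic outcomes at the 6- and 12-month follow-ups among the four groups". The second is matched and applies at 12 months only: "In addition, Cochrans Q test was applied to compare the clinical and radiographic success rates of the four pulpotomy materials". For Q it adds: "The test was calculated using data from all 22 patients in each group". One criterion covers everything: "The significance level was set at" p < 0.05.

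The document does not say which test answers the primary objective, how the two outcomes are combined into a conclusion, or whether Q is exact or asymptotic. Beyond success and failure rates, it plans no two-material comparison, estimated difference or confidence interval.

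**The concern.** Under the split-mouth design the same 22 children supply all four groups. Fisher's exact test on a 4 by 2 table assumes 88 independent teeth, which this design does not provide. Q conditions on the child and is the test that fits. Because Q is only added to Fisher, each 12-month outcome has two p-values and no rule for choosing between them, so the choice could be made after both are seen.

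Two further gaps follow. Two unranked outcomes at 0.05 each can push the overall false-positive rate above 5% if either may count as a finding. And both tests are omnibus: a significant result says that the four materials are not all alike, but does not say which one differs or by how much, although comparing the materials is the stated aim.

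**Working it through.** **Inputs.** From the document: 22 children with four teeth each, two outcomes at 12 months, level 0.05. The plan states no p-value, failure rate or error rate on this point, so there is no figure of its own to reproduce. The minimum of 19 patients in Section 3 is not used. All failure rates and clustering strengths below are assumptions.

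**1. Same totals, opposite verdicts.** Take failures of 1, 2, 3 and 7 out of 22 (total 13, sum of squares 1 + 4 + 9 + 49 = 63).

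- Fisher uses only the totals: p = 0.103 for every arrangement.
- Q = 3 × (4 × 63 − 13²) / (4 × 13 − S) = 249 / (52 − S), where S is the sum of squared failures per child, on 3 df.
- Thirteen children with one failure each: S = 13, Q = 249/39 = 6.385, p = 0.094 (exact 0.116).
- Fully nested in 7 children (4, 3, 2, 1, 1, 1, 1 failures): S = 33, Q = 249/19 = 13.105, p = 0.0044 (exact 0.0039).
- Over all arrangements, exact Q is below 0.05 whenever 7 or 8 children are affected, mixed at 9 or 10, and never below 0.05 at 11 or more. These are counts of patterns, not probabilities.

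**2. The version of Q matters when failures are few.** Take 3, 0, 0 and 0 failures.

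- Fisher: 4 × C(22,3)/C(88,3) = 4 × 1540/109736 = 0.056.
- Asymptotic Q: 3 × (4 × 9 − 9)/(4 × 3 − 3) = 9.0, p = 0.029.
- Exact Q: 4 × (1/4)³ = 0.0625.

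**3. How often the tests disagree (simulated, asymptotic Q).** Failures come from a latent normal model; the child share is the part of the variance common to a child's four teeth. Three materials have clinical/radiographic failure between 3/5% and 10/20%, and the fourth between 15/30% and 35/50% (one setting 20/25%). Disagreement on at least one outcome:

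- child share 0: 8.9-21.4%
- child share 0.3: 20.1-29.1%
- child share 0.6: 33.6-43.8%

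The direction is mostly Q significant and Fisher not. For a single outcome with failure 5/5/20/30% and child share 0.6, Fisher's power is 58% and Q's 78%. With no true difference, disagreement on at least one outcome is about 2-7%.

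**4. False positives if either outcome may count (simulated, no true difference).** Two asymptotic Q tests at 0.05, by clinical/radiographic failure:

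- 3/5%: 3.7-4.8% at child share 0 to 0.3; 1.9-2.2% at 0.6
- 5/10%: 5.9-6.8%; 4.2-4.7% at 0.6
- 10/20%: 7.7-8.7%; 6.5-7.1% at 0.6
- 20/30%: 8.6-9.2% at child share 0 to 0.3

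Adding the two 12-month Fisher tests raises the highest figure from 9.2% to 10.5%, which is 1.3 points of a 5.5-point excess over 5%; a separate run gave 1.8 of 5.7. Most of the excess therefore comes from having two outcomes.

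**5. What pairs of materials could show.** Four materials make six pairs per outcome; 0.05/6 = 0.0083. With all discordant children in one direction, exact McNemar p = 2 × 0.5^d: d = 7 gives 0.0156, d = 8 gives 0.0078. So 8 such children of 22 are needed.

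**The case against.** The best defence is that the right analysis is already there: Q is applied to both outcomes at exactly the time point of the objective, and if both tests are reported, no p-value is hidden. That is true, but being in the plan does not make Q the test that decides.

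Second, the example in step 1 needs clustering. If those 13 failures fall independently across children, exact Q is below 0.05 in only about 6% of arrangements (mean 10.8 children affected). This stands: the example shows what can happen, not what usually does. Likewise, most disagreements are differences that Fisher misses, which is lost sensitivity rather than a false claim.

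Third, clinical and radiographic success may be meant as two separately reported questions. The objective does not say that either alone would count, so the false-positive figures apply only under that rule. A rule requiring both would remove the inflation.

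A reader might also infer that six tests at 0.05 carry a false-positive risk of 1 − 0.95⁶ = 26.5%. The documents do not support this: the 6-month Fisher tests lie outside the 12-month objective, and the two 12-month tests of an outcome use the same data and are strongly dependent. Nor does using Fisher mean that false positives multiply. With child share 0.6 and no true difference, it rejects in only about 0.5% of trials per outcome.

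**Conclusion.** The point holds and should be fixed. Fisher's independence assumption is wrong for teeth randomized within a child, and the plan leaves undefined which of two possibly conflicting results answers the primary objective. The assumed scenarios with one worse material put disagreement at roughly 10-20% of trials without clustering and 35-45% with strong clustering. With no true difference it is about 2-7%.

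The effect on false positives is smaller and conditional. If either outcome may count, two Q tests give about 2-9%: above 5% at moderate failure rates, but not when failures are rare, nor at 5/10% failure with strong clustering. Fisher adds at most about 2 points. The scenarios with the most disagreement are not those with the most false positives.

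That no difference can be attributed to a particular material rests on no assumption; it follows from both tests being omnibus. It would go too far to conclude that the plan ignores the matching, or that a favourable test was selected: Q is planned, and the document reports no results.

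**What to change.** Rewrite Section 7 as follows.

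- Cochran's Q at 12 months is the only deciding test for each outcome. State the exact version, since failures may be few. Drop Fisher as an inferential test.
- State one rule for the two outcomes. If either may count, Holm is one option: the smaller p against 0.025, then the other against 0.05. In simulations with child share up to 0.3, exact Q with Holm gave 0.6-4.4% false positives. If both are required, no adjustment is needed.
- Label the 6-month results descriptive.
- For each outcome, report the paired risk difference with 95% CI for the six material pairs, as unadjusted estimates that do not declare a difference.
- Declare a pairwise difference only by McNemar's exact test, after a significant Q for that outcome, adjusted over the six pairs at the level at which Q was rejected.
- Section 7 is in the past tense. If results are known, report this as a dated, disclosed post hoc re-analysis; the gain is then clearer reporting, not restored error control.

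Exact Q, Holm and the McNemar step are partly preference. The essential parts are one matched deciding test, a stated rule for the outcomes, and matched pairwise estimates.

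**Cost.** No new data are needed. In the simulations, exact Q had 1-10 points less power than asymptotic Q, and Holm lowered the chance of at least one significant outcome by 6-11 points. Exact Q still had at least Fisher's power in all 24 comparisons with one worse material. Pairwise power is low: 8 one-directional discordant children at 0.05/6, or 9 at 0.025/6 (p = 0.0039). Intervals are wide (Tango: −15 to +15 points with no discordant pairs) and can part from the test: with 4 discordant children, all one way, the interval is +0.6 to +38.5 points but McNemar p = 0.125. With no true difference, at least one of the twelve intervals excludes zero in 6-35% of simulated trials, so they must not be used to declare differences.
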